Women of child-bearing potential must be informed that taking the study treatment may involve unknown risks to the fetus if pregnancy were to occur during the study, and agree that in order to participate in the study they must adhere to the contraception requirements outlined in the exclusion criteria. If there is any question that the participant will not reliably comply, they should not be entered or continue in the study.

Participants may not be able to come to on-site visit in case of COVID-19 pandemic restrictions. If participants are unable to come to their study site for scheduled visits due to COVID-19 pandemic, investigator should contact the participant via phone call or conduct virtual contacts (e.g., teleconsult) for safety monitoring.

The risk to participants in this trial may be minimized by compliance with the eligibility criteria and study procedures, as well as close clinical monitoring.

Canakinumab is known to be highly effective and safe for patients with SJIA which is a similar disease to AOSD. Data from the pooled analysis of clinical trials in SJIA patients demonstrate similar efficacy and safety profiles of canakinumab throughout the age groups (2 to <12 years, 12 to <16 years, and 16 to <20 years). $\geq 70\%$ of SJIA participants achieved adapted ACR Pediatric 30 response across age groups at Day 15, and the response rate remained similar across age groups until Day 85. An investigator-initiated trial in non-Japanese AOSD patients (Study GDE01T) consistently showed trends toward greater improvement in efficacy endpoints, such as improvement in DAS28-ESR and ACR response rate, in the canakinumab group compared with the placebo group, although statistical significance was not achieved. Additionally, a

comparison of the Study GDE01T data and the SJIA pooled dataset showed that the adapted ACR 30 response rate in canakinumab treatment was similar in AOSD and SJIA patients. Taken together, canakinumab was considered effective for AOSD as well as for SJIA.

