5.2 Exclusion criteria

Participants meeting any of the following criteria are not eligible for inclusion in this study

1. Pregnant or nursing (lactating) female participants, where pregnancy is defined as the state of a female after conception and until the termination of gestation, confirmed by a positive hCG laboratory test ($> 5 \text{ mIU/ mL}$) at screening visit
2. For female participants of child-bearing potential defined as all females physiologically capable of becoming pregnant, unless they are using effective methods of contraception during administration of study treatment. Effective contraception methods include:
 - Barrier methods of contraception: male or female condom or occlusive cap, diaphragm or cervical/vault caps.
 - Other more effective forms such as oral, injected or implanted hormonal methods of contraception or placement of an intrauterine device (IUD) or intrauterine system (IUS), or other forms of hormonal contraception that have comparable efficacy (failure rate $< 1\%$), for example hormone vaginal ring or transdermal hormone contraception or total abstinence or male/female sterilization

Note: Women of non-childbearing potential is defined as women who are physiologically and/or anatomically incapable of becoming pregnant, as now further described:

- They are post-menopausal as evidenced by 12 months of natural (spontaneous) amenorrhea with an appropriate clinical profile (i.e., age appropriate history of vasomotor symptoms).
- They have had bilateral surgical oophorectomy (with or without hysterectomy), total hysterectomy or bilateral tubal ligation at least six weeks prior. In the case of oophorectomy alone, only when the reproductive status of the woman has been confirmed by follow up hormone level assessment is she considered not of childbearing potential.

In case local regulations deviate from the contraception methods listed above, local regulations apply and will be described in the informed consent form (ICF).

3. Use of other investigational drugs at the time of enrollment, or within 30 days or 5 half-lives of enrollment, whichever is longer.
4. History of significant hypersensitivity to study drug or to biologics.
5. History/evidence of active MAS or disseminated intravascular coagulation (DIC) within 6 months of enrollment.

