6.1 Study treatment

6.1.1 Investigational and control drugs

Participants will receive canakinumab 4 mg/kg (maximum of 300 mg) administered subcutaneously every 4 weeks at the study site throughout the study.

ACZ885 150 mg: Active canakinumab in individual 2 mL glass vials, each containing 150 mg canakinumab liquid in vial (Table 6-1).

Table 6-1 Investigational drug

Investigational Drug	Pharmaceutical Dosage Form	Route of Administration	Presentation	Sponsor (global or local)
ACZ885 150 mg	Solution for Injection	Subcutaneous Injection	Open label supply in vials	Sponsor (global)

The maximal total single dose of canakinumab allowed is 300 mg in one day, which is administered as two subcutaneous 150 mg injections once every 4 weeks.

Novartis will provide canakinumab until canakinumab is approved for ASD in Japan or Novartis terminates the study.

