7.1 Pediatric Assent

In pediatric participants (< 20 years of age) parental permission and, whenever possible, pediatric assent is needed instead of the procedure for informed consent used for research involving adults. In general, one or both parents or a guardian must be provided with the information ordinarily required for informed consent, so that they may decide whether to allow the child to participate, and children capable of assent must also express their willingness to participate. These forms will be submitted for IRB/IEC approval.

8 Visit schedule and assessments

The Assessment Schedule ([Table 8-1](#)) lists all of the assessments and when they are performed. All data obtained from these assessments must be supported in the participant's source documentation.

Participants should be seen for all visits/assessments as outlined in the assessment schedule ([Table 8-1](#)) or as close to the designated day/time as possible. Missed or rescheduled visits should not lead to automatic discontinuation.

Participants who discontinue from study treatment are to return for the end of treatment visit as soon as possible, and attend the follow-up visits as indicated in the Assessment Schedule.

Participants who discontinue from study or withdraw their consent/oppose the use of their data/biological samples should be scheduled for a final evaluation visit if they agree, as soon as possible, at which time all of the assessments listed for the final visit will be performed. At this final visit, all dispensed investigational product should be reconciled, and the AE and concomitant medications not previously reported must be recorded on the CRF.

As per [Section 4.6](#), during a Public Health emergency as declared by Local or Regional authorities i.e. pandemic, epidemic or natural disaster that limits or prevents on-site study visits, alternative methods of providing continuing care may be implemented by the investigator as the situation dictates. If allowable by a local Health Authority and depending on operational capabilities, phone calls, virtual contacts (e.g. tele consult) or visits by site staff/ home nursing

staff to the participant's home, can replace on-site study visits, for the duration of the disruption until it is safe for the participant to visit the site again.

Period	Screening	Treatment																

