8.4.3 Pregnancy and assessments of fertility

All pre-menopausal women who are not surgically sterile will have pregnancy testing. Additional pregnancy testing might be performed if requested by local requirements.

Female participants of child-bearing potential must be informed of the need to prevent pregnancy during the study. Please refer to [Section 5.2](#) for effective contraception methods. A

serum pregnancy test is required at Screening. Urine pregnancy tests will be performed as indicated in [Table 8-1](#).

If participants cannot visit the site to have serum pregnancy tests during a Public Health emergency as declared by Local or Regional authorities i.e. pandemic, epidemic or natural disaster, that limits or prevents on-site study visits, urine pregnancy test kits may be used. Relevant participants can perform the urine pregnancy test at home and report the result to the site. It is important that participants are instructed to perform the urine pregnancy test first and only if the test result is negative proceed with the administration of the study treatment. A communication process should be established with the participant so that the Site is informed and can verify the pregnancy test results (e.g., following country specific measures).

Assessments of fertility

Medical documentation of oophorectomy, hysterectomy, or tubal ligation must be retained as source documents. Subsequent hormone level assessment to confirm the woman is not of child-bearing potential must also be available as source documentation in the following cases:

1. Surgical bilateral oophorectomy without a hysterectomy
2. Reported 12 months of natural (spontaneous) amenorrhea with an appropriate clinical profile.

In the absence of the above medical documentation, Follicle Stimulating Hormone (FSH) testing is required of any female participant regardless of reported reproductive/menopausal status at screening/baseline.

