9.1 Discontinuation from study treatment and from study

9.1.1 Discontinuation from study treatment

Discontinuation of study treatment for a participant occurs when study treatment is permanently stopped for any reason (prior to the planned completion of study treatment administration, if any) and can be initiated by either the participant or the investigator.

The investigator must discontinue study treatment for a given participant if, he/she believes that continuation would negatively impact the participant's well-being.

Discontinuation from study treatment is required under the following circumstances:

- Participant/guardian decision
- Pregnancy
- Use of prohibited treatment as per recommendations in the prohibited treatment section
- Any situation in which continued study participation might result in a safety risk to the participant
- Any severe or serious adverse event that is not compatible with administration of study medication, including adverse events that require treatment with an unacceptable co-medication
- Onset of malignancy
- Occurrence of uncontrolled life-threatening infection
- Any other protocol deviation that results in a significant risk to the participant's safety

The investigator should consider discontinuing participants from study treatment who experience a clinically important worsening of disease activity compared to baseline at two consecutive visits after Week 4. A clinically important worsening will be defined as participants who do not meet the adapted ACR30 criteria by Week 12 or participants with non-response (defined as Adapted ACR <30) at two consecutive visits at any time in the study beginning at Week 12.

All participants who discontinue will complete an EOS visit, be discontinued from the trial and be treated as per standard local medical practice (see also [Section 10.1.3](#) for information on SAE reporting following the last dose of study medication).

If discontinuation from study treatment occurs, the investigator should make a reasonable effort to understand the primary reason for the participant's discontinuation from study treatment and record this information.

Participants who discontinue from study treatment agree to return for the end of treatment and follow-up visits indicated in the Assessment Schedule (refer to Section 8).

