If the participant cannot or is unwilling to attend any visit(s), the site staff should maintain regular telephone contact with the participant, or with a person pre-designated by the participant. This telephone contact should preferably be done according to the study visit schedule.

After discontinuation from study treatment, at a minimum, in abbreviated visits, the following data should be collected at clinic visits or via telephone/email contact:

- New / concomitant treatments
- Adverse Events / Serious Adverse Events

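### The visible protocol sets no contraception period after the last canakinumab dose, so a woman who stops early can be released from the duty before the last 4-week dosing interval ends

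*Protocol*

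**What the plan says.** The operative rule is in Protocol Section 5.2, item 2. Women of child-bearing potential are excluded "unless they are using effective methods of contraception during administration of study treatment".

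The other places that mention the duty add no duration:

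- Section 4.5 tells women that "they must adhere to the contraception requirements outlined in the exclusion criteria". The reason given is that "taking the study treatment may involve unknown risks to the fetus if pregnancy were to occur during the study".
- Section 7 repeats the duty to follow the contraception requirements.
- Section 8.4.3 says: "Female participants of child-bearing potential must be informed of the need to prevent pregnancy during the study". For methods it refers to Section 5.2.

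On dosing, Section 6.1.1 states: "Participants will receive canakinumab 4 mg/kg (maximum of 300 mg) administered subcutaneously every 4 weeks at the study site throughout the study".

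On stopping, the opening of Section 8 says: "Participants who discontinue from study treatment are to return for the end of treatment visit as soon as possible". Section 9.1.1 says that everyone who discontinues completes an EOS visit and leaves the trial. It also says: "Participants who discontinue from study treatment agree to return for the end of treatment and follow-up visits indicated in the Assessment Schedule". If visits are not attended, "the site staff should maintain regular telephone contact with the participant".

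Two safety windows are counted from the last dose: a follow-up call at 30 days (Section 9.3) and SAE reporting for 8 weeks (Section 10.1.3). Neither is linked to contraception.

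**The concern.** An injection given every 4 weeks is meant to act for about 4 weeks. A rule tied to administration of treatment, or to being in the study, need not last that long once a woman stops. She could follow the protocol as written, give up contraception at her final injection or at an early EOS visit, and conceive while that dose is still within its dosing interval. The protocol itself calls the risk to a fetus unknown.

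Women who remain on treatment are covered. The gap opens only at exit. Because treatment is open-ended (Section 6.1.5), the date of the last dose often cannot be known in advance, so a stated end date for the duty matters most then.

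The existing safeguards act after conception. Urine tests at visits (Table 8-1, footnote 6), stopping treatment for pregnancy (Section 9.1.1) and pregnancy reporting (Section 10.1.4, no end date given) detect or record a pregnancy; they do not prevent one. The minimum data listed in Section 9.1.1 for abbreviated visits or telephone contact are treatments and adverse events, so contraception need not come up.

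**Working it through.** The plan gives no post-dose contraception figure to reproduce. The check is calendar arithmetic on the windows it does give.

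**Inputs**

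- Dosing interval: 4 weeks (Section 6.1.1), 4 × 7 = 28 days. The 4-weekly visit days in Table 8-1 (1, 29, 57, … 337) are 28 days apart throughout.
- Safety call: day 30 after the last dose (Section 9.3).
- SAE window: 8 weeks (Section 10.1.3), 8 × 7 = 56 days. Used for reference only.
- EOS visit: no fixed distance from the last dose. Table 8-1 lists it as day 9999, and Section 8 asks only for a prompt return. Its day, k, is therefore an assumption.

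**Formula.** Let c be the number of days after the last dose on which the duty ends. Days of the last interval left uncovered = max(0, 28 − c).

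| Reading of when the duty ends | c | Uncovered days of the last interval |
|---|---|---|
| At the final injection (narrowest reading of exclusion 2) | 0 | 28 − 0 = 28 |
| At EOS, k = 7 (assumed) | 7 | 28 − 7 = 21 |
| At EOS, k = 14 (assumed) | 14 | 28 − 14 = 14 |
| At EOS, k = 28 or later | ≥ 28 | 0 |
| At the end of the dosing interval | 28 | 28 − 28 = 0 |
| At the 30-day call | 30 | 0 (day 30 is past day 28) |

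The range is 0 to 28 days.

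**For reference, against the SAE window:** 56 − 0 = 56 days if the duty ends at the final injection, 56 − 28 = 28 if at the end of the interval, and 56 − 30 = 26 if at the 30-day call.

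**Does the wider reading fix a period?** Suppose the duty runs for the whole study. The SAP's on-treatment period (Section 2.1.1) runs to EOS, but that is an analysis definition, and EOS is not tied to the last dose. Section 9.1.1 both takes a discontinuing participant out of the trial after EOS and expects her at follow-up visits, so the end of the study for her is itself unclear. This reading can shorten the gap, even to 0, but it still sets no number of days.

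**The case against.** The strongest reply is that the narrow reading is the less natural one. Under a 4-weekly regimen, administration of treatment most naturally means the whole course. Section 3 defines only a screening and a treatment epoch, and Section 8.4.3 extends the message to the whole study. Doses are given at 4-weekly visits, so a woman who stops at a scheduled visit, before the dose due that day, is already about 28 days past her last one. Her gap is then about 0. This stands: 28 days is an upper bound, and the documents do not show that it is typical. It does not help the woman who stops between visits and is seen promptly.

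Second, the consent form is a separate document (Section 7), is not available here, and may already give a duration. Part of Table 8-1 is also missing from the text. This stands too: the claim is limited to the visible protocol. The pointer to the consent form in Section 5.2 concerns locally deviating methods, so it does not settle duration either way.

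Third, a dosing interval does not measure fetal exposure, and the 8 weeks come from SAE reporting. A reader might infer that the protocol recognises an 8-week washout, or that conception within 8 weeks is unsafe. The documents support neither: they give no half-life for canakinumab and no unsafe period.

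Fourth, few women may be affected. Enrollment has stopped (Section 5), some women may move to commercial drug so that the last study dose is not their last exposure, and changing an eligibility criterion does nothing for those already enrolled. All of this is fair. It limits the scale, and it means the operative text belongs in Section 8.4.3 and in direct communication with the women concerned.

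**Conclusion.** The point holds as an omission in the visible protocol: no contraception period is stated after the last dose, and on either reading of the existing text the duty can end before the last 4-week interval does. The size is 0 to 28 uncovered days per woman of child-bearing potential who stops, depending on the reading and on the assumed day of EOS.

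A reader might conclude that every such woman has a 28-day gap. The documents do not support that, because 28 days requires the duty to end at the final injection itself. Nor do they show that women were told no duration, since the consent form may state one.

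At most 14 participants are concerned (SAP Section 2.5.6 refers to all 14). The number of women of child-bearing potential still on treatment is not given and could be zero. The efficacy analysis is unaffected. The change is worth making because the protocol calls the fetal risk unknown and the remedy is small.

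**What to change.** Add to Section 8.4.3: *Effective contraception (methods in Section 5.2) is required during study treatment and for 8 weeks after the last dose of canakinumab.* Give the justification for the period.

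- The period should be no shorter than the 4-week dosing interval. Eight weeks is a provisional default that matches Section 10.1.3; replace it if the sponsor's elimination data support a different period.
- If the consent form already gives a justified duration, use that one.
- Align exclusion 2 for consistency, and put the same period in the consent form.
- Tell women of child-bearing potential still on treatment by letter or consent update, since the eligibility text no longer reaches them.
- Restate the end date at the EOS visit and at the 30-day call.

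The cost is one sentence, one clause and one consent-form line by written amendment (Section 14.1), plus a letter or consent update for a few women. With 8 weeks, the duty lengthens by 56 − 0 = 56 days over the narrowest reading, or 56 − 28 = 28 days if it is already read to the end of the dosing interval.

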6.1 Study treatment

6.1.1 Investigational and control drugs

Participants will receive canakinumab 4 mg/kg (maximum of 300 mg) administered subcutaneously every 4 weeks at the study site throughout the study.

ACZ885 150 mg: Active canakinumab in individual 2 mL glass vials, each containing 150 mg canakinumab liquid in vial (Table 6-1).

Table 6-1 Investigational drug

Investigational Drug	Pharmaceutical Dosage Form	Route of Administration	Presentation	Sponsor (global or local)
ACZ885 150 mg	Solution for Injection	Subcutaneous Injection	Open label supply in vials	Sponsor (global)

The maximal total single dose of canakinumab allowed is 300 mg in one day, which is administered as two subcutaneous 150 mg injections once every 4 weeks.

Novartis will provide canakinumab until canakinumab is approved for ASD in Japan or Novartis terminates the study.

6.1.2 Additional study treatments

No other treatment beyond investigational drug and control drug are included in this trial.

6.1.3 Supply of study treatment

Not applicable.

6.1.4 Treatment arms/group

All participants will receive canakinumab as open-label study medication.

Participants will be administered canakinumab 4 mg/kg every 4 weeks. The maximum total single dose of canakinumab allowed is 300 mg. Any participant who requires a dose greater than a single dose of 150 mg (participants > 37.5 kg) will require two s.c. injections.

6.1.5 Treatment duration

The planned duration of treatment is at least 48 weeks. The study allows participants to continue canakinumab treatment until it is approved for ASD and is commercially available for clinical use in Japan or Novartis terminates the study. Participants may be discontinued from treatment earlier due to unacceptable adverse event (AE), disease progression and/or treatment is discontinued at the discretion of the investigator or the participant.

6.2 Other treatment(s)

6.2.1 Concomitant therapy

All medications, procedures, and significant non-drug therapies (including physical therapy and blood transfusions) administered after the participant was enrolled into the study must be recorded on the appropriate Case Report Forms.

Each concomitant drug must be individually assessed against all exclusion criteria/prohibited medication. If in doubt, the investigator should contact the Novartis medical monitor before randomizing a participant or allowing a new medication to be started. If the participant is already enrolled, contact Novartis to determine if the participant should continue participation in the study.

6.2.1.1 Permitted concomitant therapy requiring caution and/or action

No concomitant use of second line agents such as disease-modifying and/or immunosuppressive drugs will be allowed with the exception of followings:

- Systemic corticosteroid treatment ≤ 1.0 mg/kg/day (maximum 60 mg/day) in 1-2 doses of oral prednisone (or equivalent). Daily dose of systemic corticosteroid treatment (≥ 10 mg AND ≤ 1.0 mg/kg/day, maximum 60 mg/day) should be stable until Week 8. Beginning at the Week 8 visit, corticosteroid dose tapering should be attempted as per corticosteroid tapering guidelines.
- Stable dose of methotrexate (maximum of 20 mg/m²/ week) and folic/folinic acid supplementation (according to standard medical practice of the center).
- Stable dose of no more than one NSAID.

Corticosteroid tapering

Participants using concomitant corticosteroids at study entry may begin to reduce their corticosteroid dose to the lowest possible dose/discontinuation beginning at Week 8 until the End of Study. All changes in corticosteroid doses should be made in the appropriate concomitant medication eCRF.

Rules for corticosteroid tapering:

- Corticosteroid tapering is encouraged and permitted to occur beginning at Week 8 if it is the investigator's judgment that a participant's AOSD disease activity is stable and has not worsened.
- As shown in [Table 6-2](#), for oral prednisone (or equivalent) doses > 0.1 mg/kg/day, the dose should be tapered at 0.1 mg/kg of oral prednisone (or equivalent) per week. If and

when the oral prednisone (or equivalent) dose is at 0.1 mg/kg/day, the dose should be reduced to 0.05 mg/kg/day of oral prednisone (or equivalent) for 1 week, then to ≤ 0.05 mg/kg/every 48 hours for the next 2 weeks and then discontinued.

- If it is the investigator's judgment that a participant's AOSD disease activity worsens during corticosteroid tapering then the participant must return to the immediate prior dose (or higher if deemed necessary by the investigator) and may not resume corticosteroid dose tapering for at least 2 weeks.

Table 6-2 Corticosteroid tapering guideline

Prednisone (or equivalent) dose	Amount of reduction
> 0.1 mg/kg/day	Taper at 0.1 mg/kg per week until at dose of 0.1 mg/kg/day
0.1 mg/kg/day	Taper to dose of 0.05 mg/kg/day for 1 week
≤ 0.05 mg/kg/day	Alternate administration days (i.e. take dose every 48 hours) for 2 weeks and then discontinue

